#### 1.4.1 Risks Associated with Related Clinical Procedures

Components of this study which generate the majority of risk to the subject include the implantation and explantation surgeries, and the percutaneous connector. Given the early stage of clinical development for the device investigated in this study, it may be useful to examine other procedures and operations which include similar components. For example, bone-anchored hearing aids (BAHAs) rely on a titanium fixture similar to the titanium percutaneous component (the percutaneous connector) used in this study; rates of infection for BAHA devices have been reported in the range of 1.0% to 5.0%, with other complications (<1%) including persistent pain, granulation tissue, and persistent bleeding (68-71). Infections which occur as a result of neurosurgery are potentially severe, but have a low incidence rate of 1.7% to 2.6% in the United States (72-78). Placement of foreign bodies (specifically, shunts), CSF leakage, age, and duration of surgery have all been implicated as being significantly associated with surgical site infections for craniotomies and other neurosurgeries (73-75, 77). Prophylactic antibiotics may play a role in mitigating the risk of infection (73). Anticipated adverse events associated with implantation of leads for epilepsy localization procedures include hemorrhage (0.8% to 2.5% of patients), infection (1.8% to 9.1%) and permanent neurological complications such as hemiparesis, aphasia, apraxia, Gerstmann syndrome, and other sensory and motor deficits (0.6% to 1.5%; transient deficits occur somewhat more frequently). Resection of epileptic tissue is associated with hemorrhage (0.7%) and infection (1.0%) and neurological deficits (about 3.3%), such as language, visual field, and motor deficits. Deep Brain Stimulation (DBS) systems are associated with hemorrhage (1.1% to 3.9%), infection (1.7% to 4%), and neurological deficits such as hemiparesis (about 1.1% to 16% of patients) (79-85).

#### 1.4.2 Risks Identified for this Study

- Excessive bleeding, fainting or feeling lightheaded, hematoma, or infection may result from having blood drawn (approximately 20cc) for pre-surgical screening. The expected frequency of these complications is rare. Blood will be drawn for pre-surgical screening in a clinical care environment, by fully trained phlebotomist, and with appropriate resources and equipment on hand to handle any complications which may arise during the procedure. The site from which blood is drawn will be thoroughly disinfected prior to the procedure, and protected afterward with antibiotic cream and bandage.
- Risk of temporary sensations of warmth or localized heating during the pre and post-surgical MRIs. The expected frequency of these complications is rare. MRI is generally accepted as a procedure which has no harmful effects on biologic tissue (86). Most complications associated with MRI have occurred because proper procedures (e.g., screening for metal objects) were not followed. MRIs will be obtained in a clinical care environment, by trained radiology technicians, and with appropriate resources and equipment on hand to provide immediate medical assistance for any discomfort or complications which may occur.
- Risks due to anesthesia, including aspiration, coughing, gagging, muscle spasms in the voice box, laryngospasm, bronchospasm, hypertension, tachycardia, damage to teeth and lips, swelling in the larynx, sore throat, hoarseness, heart attack, stroke, awareness during anesthesia, as well as unanticipated allergic reaction, and possibly death. The expected frequency of these complications is low. Anesthesia will be performed by a trained and board-certified anesthesiologist in the controlled medical environment of the operating suite. The subject's vital signs will be closely monitored during the entire procedure to watch for signs of complications due to anesthesia. The appropriate equipment and personnel will be available in the operating room to respond to any complications due to anesthesia.
- Intracranial hemorrhage, subdural hematoma, or epidural hematoma could result in headache, seizures, stroke, temporary or permanent neurologic impairment such as weakness, sensory loss, or coma, change in consciousness, or death. The expected frequency of these complications is low: reports of neurosurgeries for the treatment of epilepsy or implantation of deep brain stimulators suggest that the incidence of bleeding may be between 0.8% and 3.9% (79-85, 87-90). The surgery will be performed by trained and board-certified neurosurgeons in a controlled medical environment. Major blood vessels will be avoided when the NeuroPort Array is implanted. The subject's vital signs will be closely monitored during the entire procedures to watch for signs of surgical complications. The appropriate equipment and personnel will be available in the operating room to respond to any complications due to anesthesia. The

surgery will be performed according to the surgical manual included in the 510(k) application for the NeuroPort Array. During the first two days of post-operative recovery period at USC the patient will undergo a CT scan to ensure that there is no bleeding from the device implantation procedure. The patients will be placed on Keppra 500 mg PO q12 hours for two weeks for routine seizure prophylaxis.

- Cerebrospinal Fluid (CSF) leakage during the surgery could result in a dull or throbbing headache or need for additional surgery, and could be a factor for increased risk of infection. The expected frequency of these complications is low. Evidence from the literature suggests that CSF leakage occurs in a low percentage of neurosurgeries: in epilepsy-related procedures, for example, the incidence of CSF leakage has been reported from 0.1% to 1.4% (88, 89). CSF leakage has been implicated as a potential factor for increased risk of infection (74). Subjects will be monitored closely intraoperatively and during post-operative critical care and throughout the study to watch for signs of CSF leakage. The attending physician will medicate pain as determined medically necessary, and will determine the appropriate response if medication is insufficient.
- Infection could occur after surgery, including meningitis (which has the potential to cause brain damage or hearing loss). The expected frequency of these complications is low: the rate of infection in similar neurosurgeries suggests that the rate of infection in this study may fall between 1.7% and 9.1%, with most reports from the last decade within the range 1.7% to 4% (79-85, 87-90). After the implantation surgery, the subject will receive critical care for a minimum of 1-2 days in the hospital. The patient will receive 24 hours of IV antibiotics post-op. During this time, the subject will be closely monitored for any signs of systemic infection and infection around the wound. If any infection occurs, the subject will receive immediate, appropriate clinical treatment.
- Short-term pain in the head or neck might occur after surgery. The expected frequency of these complications is moderate. The subject will likely experience discomfort in the head and neck due to the nature of the surgery. This pain will be short-term, and should dissipate during the post-operative critical care period, or during the healing period. The attending physician will review each subject's condition individually to determine whether the discomfort requires pharmacological intervention or other response.
- Allergic reaction to the implanted devices is possible. The expected frequency of this complication is low. The NeuroPort Arrays are manufactured using biologically-safe materials, and have a documented history of being implanted both acutely and chronically without incidence of allergic reaction. The NeuroPort Arrays are cleared under 510(k) approval for implantations of less than 30 days. Subjects will be monitored closely during surgery, during the post-operative critical care period, and throughout the study to watch for signs of allergic reaction to the implanted device. If symptoms occur, they will be evaluated by the attending physician, who will determine the proper response (ranging from medication to explantation and exit from the study).
- Discomfort or lack of healing of the skin area could occur at or around the site of the implanted percutaneous connector. The expected frequency of occurrence for this complication is moderate. In studies of bone-anchored hearing aids, severe skin irritation or infection has been reported in 1.0% to 5.0% of all observations (68-70). However, low-to-moderate skin irritation or infection (i.e., treatable via medication) has a higher rate of incidence – 5.1% to 14.0% (68, 71). The wound site will be carefully monitored at all stages of the study, and the subject questioned, to detect signs of discomfort or inadequate healing. Such symptoms and conditions will be treated appropriately and immediately at the direction of the attending physician.
- Tissue damage and histological responses could lead to functional deficits and increased long-term risk of neurological disorder. The expected frequency of these complications is low. When subdural electrode strips are placed to localize epileptogenic tissue, transient neurological deficits have been reported in 5.6% to 11.1% of cases (87, 89). For tissue resection, rates of transient neurologic deficit increase to 8.6% to 30% (90, 91). Permanent neurologic deficits due to stereotactic electrode placement are rare, reported at 0.6% to 1.5% (85, 87, 91). The NeuroPort Arrays are small (4 mm x 4 mm) and short (electrodes are 1.5 mm in length), and will displace or damage small amounts of tissue. During the study, the subject will be monitored on a daily basis by caregivers, and evaluated regularly by physicians, to watch for seizures, loss of function, change in function or behavior, or any other signs of complications. If any appearing symptoms are specified as exit criteria, the patient will be explanted and exit the study.

Otherwise, the attending physician will judge whether conditions are serious enough to warrant explantation.

- Chronic risk of infection associated with the implanted device. The expected frequency of this complication is low. In studies of bone-anchored hearing aids, severe skin irritation or infection has been reported in 1.0% to 5.0% of all observations (68-70). However, low-to-moderate skin irritation or infection (i.e., treatable via medication) has a higher rate of incidence – 5.1% to 14.0% (68, 71). Wound care will be performed regularly and will be monitored on a daily basis by the caregiver, and evaluated regularly by a physician. Excess redness, swelling, drainage, inflammation, or bleeding will be reported to the physician for appropriate urgent follow up care. If the subject experiences any allergic reaction to wound cleaning materials, appropriate substitutes will be found. During the course of the study any infections deemed minor or superficial in nature by the attending physician will be treated and monitored. An infection deemed serious in nature by the attending physician is a withdrawal criterion for the study (Section 4.2.4) and would result in immediate explantation and treatment of the infection.
- The subject will be conducting tasks involving electrical and/or mechanical equipment which could harm the subject. The expected frequency of this complication is low. End effectors, whether physical or virtual, will be electrically and mechanically isolated from the patient so that no physical or electrical harm to the subject could result from use of the effector. The NeuroPort Biopotential Signal Processor receives data from the NeuroPort Array via an optically isolated amplifier. Thus, electrical phenomena have no path from an end effector, physical or virtual, back to the NeuroPort Array. In the case of the physical effector, the physical device would be placed sufficiently distant from the subject so that no contact is possible during task behavior or otherwise. Additionally, an emergency stop button would be available to the operating technician which will immediately remove power from the physical effector.
- The subject could experience frustration while trying to learn brain control in the study sessions. The expected frequency of this complication is low. We intend to select a subject who is mentally and emotionally able to participate despite the rigors of participation. Subject inclusion/exclusion criteria include: stable psychosocial support system, sufficient decision-making capacity, memory, and intellectual capabilities, and no evidence of psychotic illness or chronic psychiatric disorders. The subject will be monitored for signs of severe stress, fatigue, or frustration. The difficulty and frequency of study tasks will be adjusted if any of these signs are observed.
- Electrostatic discharge (ESD) from electrical contacts in the percutaneous pedestal connector presents a risk to the subject. The expected frequency of this complication is low. Electrode contacts in the percutaneous connector are electrically isolated from other metal components of the percutaneous connector and only ESD through the electrode contacts constitutes a concern; any discharges into the metal pedestal will dissipate through the skin as normal. The subject will be instructed to leave the pedestal cap, which protects the electrical contacts, in place. Only study investigators will be allowed to remove the cap for recording during study sessions. Study investigators will be trained in how to properly remove and replace the pedestal cap in order to avoid ESD. The connector on the patient cable is designed to dissipate ESD during mating in order to reduce risks and minimize patient discomfort.
- Headache and pain. The expected frequency of this complication is moderate. Post-operative pain will be managed with pain medications and will be evaluated regularly during post-operative follow up with the physicians. Additionally, the caregiver and study personnel will perform basic monitoring on a more frequent basis and report any symptoms to physicians promptly for proper care.
- Tissue response to the implanted device may cause a reduction in, or complete inability to, record neural signals. The expected frequency of this complication is moderate. The histological response of brain tissue to implanted electrodes is well studied and has been implicated in a reduction in the quality of neural signals recorded over time (52-56, 92). However, the BrainGate and BrainGate clinical studies have demonstrated neural control using a NeuroPort Array after 1,000 days of implantation (7), and other nonclinical studies have demonstrated useful signals from chronic neural implants primates (56, 93-101). These results suggest that even with a reduction in signal quality, the NPS may still be viable as a neural interface.
- The device may stop working on its own. Because the NPS is an electromechanical system, it is possible that some component of the system may break and cause the device to stop working. The device is

manufactured under a quality control system (Blackrock Microsystems), which reduces the chance of the device malfunctioning on its own. Because the NPS comprises two NeuroPort Arrays, if one breaks the other will still be able to provide neural signals. In that situation, the functionality of the NPS may be reduced and the study tasks and outcomes will be adjusted accordingly, but still to address the safety and effectiveness of the device.

#### 1.4.3 Justification for Study

The novelty of this study is that we intend to explore the safety and effectiveness of a long-term, cognitive neural implant. This novelty is manifest in two primary aspects of the study: first, that we will implant NeuroPort Arrays for a period of one year; and second, that we intend to use signals from posterior parietal cortex, which are involved in high-level plans for reaching and grasping. The nature of these signals is such that other benefits may be derived, such as bimanual control, fast learning, fast adaptation, and dexterous manipulation of virtual or physical end effectors. We have structured this study to explore both the safety and the effectiveness of such a device.

The primary risk to subjects in this study is that of infection. A reasonable expectation of the risk of chronic infection may be derived from the literature regarding bone-anchored hearing aids. Similarly to the NPS, these devices use a bone-affixed titanium implant which remains exposed through the skin. Rates of serious infection (i.e., requiring surgical intervention) associated with these similar devices range between 1.0% and 5.0%; rates of low or moderate infection (i.e., treatable extraoperatively) range from 5.1% to 14.0%. While the implants are not exactly the same (e.g., no osseointegration for the NPS), the materials and chronic, through-the-skin nature of the two implants suggests that similar rates of infection might apply to this percutaneous connectors in this study. With procedures in place to carefully monitor for signs of irritation and infection, it is our view that this risk is acceptable in the context of the benefits to be derived from the study.

Other significant risks are associated with anesthesia and surgeries to implant and explant the device. This section has presented data from the literature describing risks and complications from other, similar clinical procedures including deep brain stimulators, neurosurgical treatments for epilepsy, and general neurosurgical data. For example, it is expected that rates of post-operative infection might fall in the range between 1.7% and 4.0%. The subjects in this study will undergo surgery with a highly skilled clinical team, and will be carefully monitored post-operatively with a standard 24-hour course of antibiotics. It is again our view that with proper management of the risk factors by an experienced team of physicians, the risks associated with anesthesia and surgery are acceptable in the context of the benefits of this study.

The safety of the device has been demonstrated extensively in the literature. Several instances of chronic implantations of NeuroPort Arrays exist in the literature for human subjects and CerePort Arrays for nonhuman primate subjects. In one report from the BrainGate trials, performance of a brain-computer interface was evaluated 1000 days after implantation in a person with tetraplegia (7); other reports from that same clinical study have not described any clinical emergencies or trauma resulting from the implantation of the NeuroPort Array or participation in study tasks (1-6, 8). Many studies exist which have evaluated data recorded with NeuroPort Arrays implanted in nonhuman primates (56, 93-101). These examples demonstrate a history of safety of the NeuroPort Array.

The effectiveness of relying on signals from the posterior parietal cortex for neural interface control has also been well established in the literature. The posterior parietal cortex (PPC) forms a juncture between sensory and motor areas and is involved in sensory-motor integration (15-17). A number of studies relying on electrophysiological, neuropsychological, and neuroimaging results have shown that in humans, areas BA5 and AIP are strongly activated during reaching and grasping (37-48). Our lab group has been instrumental in advancing an understanding of the cognitive signals available in the posterior parietal cortex (14, 19, 27, 28, 31, 57, 58, 67, 102-105).

The proposed study will allow us to perform long-term brain-computer interface training, which takes advantage of neuroplasticity to enhance volitional control over neural activity. The information that is learned will provide a basis for the development of fully-implantable brain-computer interfaces that can control complex assistive technologies. Our main long-term goal, to utilize signals from chronic neural recordings to control external assistive devices, is likely to be perceived as a significant benefit by the targeted patient population. Individuals with high cervical spinal lesions consider restoration of hand and arm function to be a top priority for improving their ability to perform activities of daily living independently (106). We believe that the potential benefits for the

targeted patient population, in concert with properly managed risk, amount to a strong justification for pursuing this clinical study.

### 1.5 Central Hypotheses

We hypothesize the following regarding the safety of the device:

- (1) Implantation will not be associated with infection or irritation;
- (2) The Severe Adverse Event (SAE) rate, calculated as the number of SAEs per implant-day, will not rise above 1% for any study subjects.

We hypothesize the following regarding the effectiveness of the device:

- (1) Control over virtual and physical end effectors, as measured by accuracy, will be significantly greater than chance when using the NPS;
- (2) Action Research Arm Test (ARAT) scores will improve over the course of the trial when controlling virtual or physical end effectors
- (3) Using the NPS with either virtual or physical end effectors will result in significant increases in the subjects' quality of life.

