### Study Synopsis

Brain signals may be used to control extracorporeal devices such as robotic effectors, prosthetic limbs, or computer systems. For paralyzed patients, a device which implements such a possibility could represent an important step forward in providing some independence and the ability to interact with the environment. This prospective, longitudinal, single-arm feasibility study will be used to evaluate the safety and effectiveness of the Neural Prosthetic System (NPS), a device designed to record brain signals from the cortex, to control physical and virtual effectors. The NPS uses electrodes which are already approved by the FDA for implantations of less than 30 days; an Investigational Device Exemption has been obtained from the FDA which allows implantation of 53 weeks in two subjects. While the NeuroPort Array has been used in other longitudinal clinical studies with similar applications, the primary advantage and differentiating feature of our study is that we will use the posterior parietal cortex to extract cognitive brain signals representing intention and planning of reaching and grasping. This study is not intended to provide immediate treatment or benefits to its participants. However, the long-term implications of the study objectives could enable new technologies to provide assistance to people suffering from paralysis.

NPS Feasibility Study	
Test Device	Neural Prosthetic System, consisting of two NeuroPort Arrays (Blackrock Microsystems, Salt Lake City, UT)
Cohort	People with high cervical spinal lesion (i.e., C4 or above)
Primary Objectives	To assess the safety and evaluate the effectiveness of the NPS as a method for paralyzed people to interact with their environment.
Device Configuration	The NPS consists of two NeuroPort Arrays. Each NeuroPort Array consists of an electrode array (100 electrodes in a 10 x 10 configuration with dimensions 4 mm x 4 mm x 1.5 mm (W x H x D); a titanium percutaneous connector, 19 mm diameter at the base.
Study Design	A longitudinal clinical feasibility study. Subjects participate in study sessions 3-5 times per week at RLANRC (their place of normal clinical care) during the study period. Each subject participates for a total of 66 weeks, including surgeries and follow-up care; the study period is 53 weeks.
Number of Subjects to be Enrolled	Two subjects will be enrolled.
Number of sites	One site, with multiple supporting institutions.

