Key Inclusion Criteria	Paralysis (high cervical spinal lesion, C4 or above) initiated at least one year prior and stable for at least 3 months prior.
Key Exclusion Criteria	Active psychiatric or medical illness which precludes surgery, stable participation in study sessions, or which requires MRI or other contraindicated procedure during time enrolled.
Primary Efficacy Objective, Analysis, and Methods	The primary effectiveness objective is to evaluate the long-term effectiveness of the NPS. The primary outcome variable is the accuracy with which tasks are performed during study sessions, which will be compared to the level of chance. The secondary outcome variable is scoring on the Action Research Arm Test, a standard test used in occupational therapy to measure upper extremity limb function following cortical damage. The tertiary outcome variable is the quality-of-life index, measured before and after the study.
Primary Safety Objective, Analysis, and Methods	The primary safety objective is to evaluate the safety of the NPS. The primary outcome variable is the presence of infection or irritation around the implant site. The secondary outcome variable is the Severe Adverse Event (SAE) rate measured per subject as a percentage of implant-days. These factors will be measured during clinical follow-up care using standard observations and exams.

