10.0 Criteria for Evaluation and Endpoint Definitions

The objectives of this study are to evaluate the safety and effectiveness of the NPS. Each of these objectives will be measured quantitatively as defined in Table 10-1 and described in this section.

Table 10-1. Safety and Effectiveness Endpoints

Objective	Hypothesis	Method of Evaluation	Time of Assessment	Comparisons Made
To evaluate the safety of the NPS implant	Primary endpoint – implantation will not be associated with infection or irritation	Inspection of subject's scalp for evidence of reddening or discharge; review of new symptoms including possible fever, headache, visual or auditory changes, or change in mood or behavior; serial neurologic exams	Immediately after implantation and weekly thereafter	The condition of the area will be compared with its condition on previous visits  History will be obtained regarding new symptoms  Neurologic exam will be compared to baseline neuro exam
	Secondary endpoint – the Severe Adverse Event (SAE) rate will not rise above 1% for any study subjects.	The SAE rate will be calculated as the number of SAEs per implant-days.	The SAE rate will be available on a daily basis throughout the study.	The SAE rate will be continuously compared to the 1% threshold level.
To evaluate the effectiveness of the NPS	Primary endpoint – patient control over the end effector (virtual or physical), as measured by accuracy, will be significantly greater than chance when using the NPS	Calculated by the NPS computer apparatus	At the end of every study session	Assessments will be compared with chance
	Secondary endpoint – Action Research Arm Test (ARAT) scores will improve over the course of the trial when controlling the virtual or physical robotic arm	ARAT administered by occupational therapists	At 10-week intervals starting at week 3.	Scores will be compared to the baseline, i.e., the first score from week 3.
	Tertiary endpoint – using the NPS with either a virtual or physical end effector will result in significant increases in the subject's quality of life	Quality of Life Inventory (QOLI) administered by the NPS operator	During prescreening (baseline) and every month subsequent to implantation	Monthly QOLI score will be compared against baseline

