### 10.2.3 Quality-of-Life Inventory

The Quality of Life Inventory (QOLI) was designed to incorporate both field-standard quality-of-life measurements as well as study-specific measurements. The QOLI is attached to this supplement as a clinical note in Section XX. In the QOLI clinical note, Section 1 is comprised of questions which are intended to capture NPS-related quality-of-life measurements. These questions were developed specifically for this study, but are potentially relevant for evaluation of other brain-controlled prostheses. Section 2 is the Satisfaction With Life

Scale (SWLS) (111), a standard questionnaire for measuring global life satisfaction. Section 3 is the Subjective Quality of Life (SQOL) (112), a single-item, subjective measure of quality of life. Both the SWLS and SQOL have been validated in populations of paralyzed patients at RLANRC. The SWLS is a standard in the field for measuring global life satisfaction. Thus, the QOLI incorporates both study-specific quality-of-life measurements as well as standard instruments for measuring life satisfaction and quality of life in paralyzed populations.

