## 13.0 Statistical Considerations

### 13.1 Study Objectives

This feasibility study is designed to evaluate the safety and effectiveness of the NPS, a device which records brain activity from the posterior parietal cortex. The safety of the device will be evaluated by monitoring the health of the implant over the course of the study. The effectiveness of the device will be evaluated by monitoring accuracy in certain tasks, as the subjects attempt use their thoughts to control external effectors, and by monitoring the subjects' quality of life, as measured by the quality-of-life index (QOLI) throughout the study. Two subjects will be enrolled in this study. Each subject will serve as his or her own control.

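### The hypothesised 'significant' rise in quality of life has no test behind it, and comparing each month with one pre-implant score would inflate false positives

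*Protocol*

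**What the plan says.** Protocol Section 1.5 states as its third effectiveness hypothesis that "Using the NPS with either virtual or physical end effectors will result in significant increases" in quality of life. Section 2.2 and the tertiary endpoint row of Table 10-1 say the same.

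Table 10-1 times the QOLI as follows: "During prescreening (baseline) and every month subsequent to implantation". The comparison is given in one line: "Monthly QOLI score will be compared against baseline".

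The schedule is stated in three ways:
- Study Synopsis: "The tertiary outcome variable is the quality-of-life index, measured before and after the study".
- Table 10-1 and the clinical calendar (Section 18.1): monthly.
- Section 10.2: every 4 weeks.

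On design, "Two subjects will be enrolled" (Synopsis) and "Each subject will serve as his or her own control" (Section 13.1 of both protocol and SAP). Section 10.2.3 describes the QOLI in three parts: study-specific questions, the Satisfaction With Life Scale (SWLS) and the single-item Subjective Quality of Life measure (SQOL). No part is named as the one to be analysed, and no total score is defined.

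Section 13.4 of both documents concedes weak power for population conclusions and calls the study a pilot. Section 13.5 treats the effectiveness objectives as met by monitoring the subjects during the tasks. Neither section says what 'significant' means for the QOLI.

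**The concern.** The hypothesis promises a statistical finding, but the stated analysis cannot deliver a valid one. A single pre-implant score carries ordinary day-to-day error. If it happens to be low, every later month looks better for the same reason, so the monthly comparisons are not separate pieces of evidence. With only one baseline value there is also no direct measure of how much the score varies before implantation.

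No rule says how the monthly comparisons combine into a conclusion, and the schedules leave open whether there is one comparison or about twelve. That choice could be made after the scores are seen. Section 13.4 says the outcomes will inform whether larger studies are warranted, and Section 13.1 names only task accuracy and the QOLI as effectiveness measures. A quality-of-life benefit reported from an unluckily low baseline would therefore carry some weight.

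**Working it through.** **Inputs from the documents.** Two subjects; one baseline QOLI per subject; repeated scores after implantation; a 53-week study period (Synopsis). The plan gives no significance level, power or effect size for the QOLI, so there is no figure to reproduce.

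**Number of follow-up scores.** Every 4 weeks: 53/4 = 13.25, so 13. Monthly (4.35 weeks per month): 53/4.35 ≈ 12.2 over the whole period, or 50/4.35 ≈ 11.5 over weeks 4–53 of Table 3-1. I use 12 and show 13 as a check.

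**Assumptions.** No true change; normally distributed scores with known within-subject SD σ; each month tested against baseline at one-sided 5%; month-to-month serial correlation ρ between 0 and 0.9 (first-order autoregressive).

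**Step 1: one monthly comparison.** The difference between a score l months after baseline and the baseline has SD σ√(2(1 − ρ^l)). With ρ = 0 a month is nominally significant if it exceeds baseline by 1.645 × √2 σ = 2.33σ. Each month alone is positive 5% of the time.

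**Step 2: any of 12 months, one shared baseline.** Given a baseline value b (in σ units) and ρ = 0, the chance that no month crosses is Φ(b + 2.33)^12. Averaging over b:

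P(any month) = 1 − ∫ Φ(b + 2.33)^12 φ(b) db = 0.27.

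For ρ > 0 the same quantity comes from simulation (300,000 runs). For either subject the formula is 1 − (1 − p)².

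| ρ | One subject | At least one of two |
|---|---|---|
| 0 | 27% | 47% |
| 0.5 | 25% | 43% |
| 0.8 | 22% | 39% |
| 0.9 | 20% | 36% |

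With 13 scores and ρ = 0 the figures are 28% and 48%. With one-sided 2.5% and 12 scores they are 16% and 29% at ρ = 0, and 12% and 22% at ρ = 0.9. Treating the 12 comparisons as independent would give 1 − 0.95^12 = 46% per subject. That overstates the rate, because the shared baseline makes the comparisons rise and fall together.

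**Step 3: what two subjects can show.**
- Sign or permutation test across subjects: smallest p = 0.5² = 0.25 one-sided, 0.50 two-sided.
- Paired t-test, 1 degree of freedom: critical t is 6.3 one-sided and 12.7 two-sided. Two-sided power is 9% at a standardised effect of 1 and 18% at 2.
- Within one subject, ranking the baseline among 13 scores: smallest p = 1/13 = 0.077. If both baselines ranked lowest, the combined p would be 1/13² = 1/169 = 0.006, but only if the 13 scores are exchangeable, with no drift and no serial correlation.

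**Step 4: would more baselines help?** The SE of (mean of 12 scores − mean of m baselines) is σ√(1/m + 1/12) with independent scores: 1.04σ for m = 1 and 0.65σ for m = 3, which is 38% smaller. Table 3-1, however, places eligibility, baseline and implantation in weeks 0 to 2. With three baselines a week apart and month-to-month correlation of 0.3, 0.5 or 0.8, the reduction relative to the middle one alone is about 10%, 6% or 2.5%.

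**The case against.** The strongest reply is that the plan never proposes these tests. Table 10-1 says only that scores are compared; it does not say that one good month counts as success. No between-subject test is planned either, since each subject is his or her own control. Quality of life is a tertiary endpoint in a two-subject feasibility study that admits weak population power. All of this is fair. It means the 20–27% and 36–47% describe one plausible reading, and that the p = 0.25 floor is background, not a criticism of a planned analysis. It does not supply a meaning for 'significant', and Section 13.4 does not reconcile that word with the design.

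Three stronger readings are tempting, and the documents do not support them:

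- **That significance is impossible.** It is not. A paired t-test can reach 5% if the two changes are nearly equal, and the rank argument in Step 3 reaches 0.006 under strong assumptions. Only sign or permutation tests across subjects have the 0.25 floor.
- **That the planned comparison is positive about nine times in ten by chance.** With exchangeable, untied scores, at least one of 12 months lies above baseline with probability 12/13 = 92%. That matters only if any rise counts as benefit, which the plan does not say. Ties, likely on the single-item SQOL, would lower it.
- **That the baseline for QOLI Section 1 is meaningless because no device is yet in place.** Section 10.2.3 says "Section 1 is comprised of questions which are intended to capture NPS-related quality-of-life measurements", but the items are not in the available text, so it cannot be judged whether they can be answered before implantation.

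**Conclusion.** The point holds in a limited form. The hypothesis of a significant increase is not supported by any specified analysis, and the one comparison that is stated, each month against one pre-implant score, is not a valid basis for it. Reading any nominally significant month as a benefit would raise a 5% error rate to about 20–27% per subject, and to about 36–47% for at least one of the two.

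Those sizes rest on one-sided 5%, 12 normally distributed scores, a known within-subject SD and serial correlation from 0.9 to 0. A different rule gives a different rate, and a single prespecified summary would remove the monthly multiplicity. A claim that the effect cannot be shown at all would go too far. Even a valid within-subject result would concern these two people and, in a single-arm study, could not be attributed to the device. The change is worth making but affects a tertiary endpoint only.

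**What to change.** 1. Remove 'significant' from the QOLI hypothesis in Sections 1.5 and 2.2 and in Table 10-1.
2. Replace the month-by-month comparison with one prespecified descriptive contrast per subject: the mean of the post-implant scores minus baseline, on the SWLS and the SQOL. Report it as an estimate without a p-value, and show the full monthly series. State which visits enter the mean, since the calendar also places a quality-of-life assessment in the follow-up phase.
3. Reconcile the QOLI schedule: before and after (Synopsis), monthly (Table 10-1 and Section 18.1), every 4 weeks (Section 10.2).
4. Optionally, repeat the QOLI at pre-implant visits already planned. The gain in precision is likely to be small because those visits fall within about two weeks.

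Items 1 to 3 change protocol and SAP wording only; item 4 would add short questionnaires at existing visits. The downside is that the quality-of-life claim becomes descriptive.
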